	7.4 STOPPING RULES	
	7.5.1 Internal Data and Safety Monitoring Board	
8	DATA HANDLING AND RECORD KEEPING	26
	8.1 CONFIDENTIALITY	26

8	3.2 SOURCE DOCUMENTS	26
8	3.3 CASE REPORT FORMS	26
8	3.4 RECORDS RETENTION	26
9	STUDY MONITORING, AUDITING, AND INSPECTING	27
9	9.1 STUDY MONITORING PLAN	
9	0.2 AUDITING AND INSPECTING	28
10	ETHICAL CONSIDERATIONS	28
11	PUBLICATION PLAN	28
12	REFERENCES	28

Study Summary

Title	A PHASE I OPEN LABEL STUDY OF THE EFFICACY AND SAFETY STUDY OF TUDCA IN ULCERATIVE COLITIS TREATMENT
Short Title	
Protocol Number	
Phase	Phase I
Methodology	Open label
Study Duration	6 Weeks
Study Center(s)	Single-center
Objectives	Primary: Determine the effect of TUDCA treatment on ER stress in colon biopsy tissues from subjects with symptomatic ulcerative colitis. Secondary: Measure the safety, tolerance and efficacy of TUDCA treatment in symptomatic ulcerative colitis.
Number of Subjects	12 (Twelve)
Diagnosis and Main Inclusion Criteria	Confirmed ulcerative colitis disease through radiographic, endoscopic and/or histologic criteria; Confirmed with moderate to severe ulcerative colitis (defined as a complete Mayo score ≥ 5 with endoscopic subscore of ≥ 1); On a stable dose of medications for IBD (i.e. no change in medication within 4 weeks of study enrollment).
Study Product, Dose, Route, Regimen	Tauroursoursodeoxycholic acid, brand name Tudcabil, Dosed in capsules containing 250 or 500mg of TUDCA for a total dose of 1.75-2g/day
Duration of administration	6 Weeks
Reference therapy	N/A
Statistical Methodology	We will be specifically interested in the statistical contrasts that compare before and after TUDCA treatment. Correlation between the primary end point and secondary end point will also be examined. The appropriateness of all analysis of variance and covariance models will be evaluated using regression residuals. If normality or homoscedasticity requirements are violated, data transformations will be explored and, if appropriate transformations cannot be found, analyses may be done semi-parametrically using the ranks of the data.

1 Introduction

This document is a protocol for a human research study. This study is to be conducted according to US and international standards of Good Clinical Practice (FDA Title 21 part 312 and International Conference on Harmonization guidelines), applicable government regulations and Institutional research policies and procedures.

1.1 Background

IBD, which includes both Crohn's disease and ulcerative colitis, is caused by a dysregulated inflammatory response to intestinal microbiota and affects approximately 1.5 million people in the United States. No medical cure currently exists and patients require a lifetime treatment with immune modulators, such as infliximab, which have significant risks and adverse effects. Strategies for developing IBD therapies face an extraordinary challenge due to our poor understanding of the disease pathophysiology. Recently, emerging evidence has demonstrated that endoplasmic reticulum stress (ER stress) and the unfolded protein response (UPR) play fundamental roles in IBD development¹⁻⁵.

The ER is the organelle in eukaryotic cells responsible for intracellular Ca^{2+} homeostasis, lipid biosynthesis and ER protein folding, transport and quality control. Alterations in the ER environment, such as altered Ca^{2+} , redox state, nutrient status, increases in the rate of protein synthesis, pathogens or inflammatory stimuli, disrupt ER protein folding causing accumulation of unfolded or misfolded proteins, a condition termed ER stress, which activates the UPR. The UPR comprises three parallel signaling branches: PKR-like ER kinase (PERK)-mediated phosphorylation of eukaryotic translation initiation factor 2α (eIF 2α), Inositol requiring enzyme 1α (IRE 1α)-mediated X-box binding protein 1 (XBP1) mRNA splicing and activating transcription factor 6α (ATF 6α) processing. The outcome of UPR activation involves transient attenuation of protein synthesis and transcriptional activation to increase the capacity for ER protein folding, trafficking and secretion, and to increase protein degradative pathways, including ER-associated degradation (ERAD) and macroautophagy. If these adaptive mechanisms cannot resolve the protein-folding defect, cells enter apoptosis 6 .

Recent studies link ER stress to the pathogenesis of IBD. Patients with active Crohn's disease and ulcerative colitis exhibit signs of ER stress in their ileal and/or colonic epithelium⁷⁻⁹. In addition, human genetic studies of IBD have identified primary genetic abnormalities in several genes including *XBP1*, *AGR2*, and *ORMDL3* that encode proteins associated with ER stress^{1, 10-13}. Previous studies indicate that cells with a high load of protein folding and secretion are sensitive to altered ER homeostasis and this can induce inflammatory response gene expression^{1, 2, 5, 14, 15}. Intestinal microbiota and their molecules stimulate IECs to increase secretion of mucins and antimicrobial peptides that can overwhelm the protein secretory capacity of IECs. Conversely, exposure to inflammatory stimuli can cause ER stress¹⁵. Upon exposure to high levels of exogenous antigens and inflammatory cytokines in the intestinal lumen, IECs may require efficient UPR-mediated ER chaperone induction to survive the heavy burden of protein folding and secretion.

1.2 Investigational Agent

Substance: Tauroursoursodeoxycholic acid, brand name TudcabilTM. (Abbreviation: TUDCA) Chemical Name: $(2-(3\alpha, 7\beta-Dihydroxy-5\beta-cholan-24oylamino)$ ethanesulfonic acid) Synthesized by Prodotti Chimici e Alimentaria S.p.A. for Bruschettini Srl, Genoa, Italy.

Manufacturing Process: Ursodeoxycholic Acid (3α , 7β -dihydroxy- 5β -cholan-24-oic acid) is considered the starting material together with Taurine (2-aminoethansulfonic acid) to be used in the production of Tauroursodeoxycholic Acid : the synthetic pathway is based on the formation of a carboamidic bond between the carboxyl group in position 24 of the bile acid and the amine group in position 2 of taurine.

TUDCA has been licensed for the treatment of cholesterol gallstones and for therapy of chronic cholestatic liver disease in Europe since 1991. From 1996-2001 at least 20,000 doses had been dispensed and no reports related to the toxicity of Tudcabil capsules had arrived during this time period (please see product profile of IND 101,296). Infrequent, but predominant side-effects in human studies (summarized in attached table) are diarrhea, headache and abdominal pain¹⁶.

Human studies relevant to this application: A pilot study conducted by [name], also at Washington University in Saint Louis, treated 10 obese, insulin-resistant adults with 1.75 g/day for 4 weeks with no adverse events¹⁷. TUDCA was given to 16 liver transplant recipients at 500 mg/day for 12 months with no drop-outs or toxicities observed. A cohort of subjects with primary biliary cirrhosis were treated with 500-1500 mg/day of TUDCA for 6 months, with diarrhea reported as the only side-effect. Several human studies have shown that use of TUDCA is well tolerated in many populations including amyloidosis¹⁶, primary biliary cirrhosis¹⁸⁻²⁰ and liver transplant²¹.

Chronic toxicity has been studied in dogs for up to 26 weeks with treatment of up to 400-600 mg/kg/day (30 x that of the proposed dose) with no observed toxicity. Rats treated with 2-20 times the proposed dose showed no evidence of carcinogenic effects after 24 months of treatment (see attached, "animal toxicity").

In summary, TUDCA has been tolerated at similar dose in humans with a variety of chronic medical conditions, with the major side-effect being mild diarrhea. The balance of the clinical information suggests that this drug is well tolerated and could have important health benefits for this study population. There are no known interactions between bile acids and immunomodelators or other IBD therapies.

1.3 Preclinical Data

We tested whether expression of ER chaperones prevent IBD development in mouse models. We found that protein misfolding in the ER caused by deletion of the ER cochaperone gene *P58*^{IPK}/*Dnajc3* exacerbates experimental colitis in mice. Furthermore, ATF6α null mice, with significant reduced expression of many ER chaperones (*Bip*, *Grp94* and *P58*^{IPK6, 22}) and hyperactivation of pro-apoptotic UPR signaling in colonic IECs, were more sensitive to experimental colitis than control mice. In contrast, we found that oral delivery of the chemical chaperone tauroursodeoxycholate (TUDCA) dramatically decreased the clinical, histological and biochemical signs of inflammation in both innate immunity- and T cell-dependent colitis through reducing ER stress signaling in colonic IECs⁴. TUDCA has been proven to facilitate protein folding and reduce ER stress both *in vitro* and *in vivo* by stabilizing protein-folding intermediates and preventing protein aggregation^{17, 23-26}. These findings indicate that ER stress plays an indispensable role in IBD development, and TUDCA administration could be a very efficient therapy for IBD patients.

In this study, we would like to bring this significant research finding from bench to the bedside. We propose to test the efficacy and safety of TUDCA in a small number (12) of symptomatic ulcerative colitis patients. TUDCA has been demonstrated as safe and well tolerated in many human clinical trials for other disease conditions. Our study will extend these findings to evaluate TUDCA's tolerance/safety in patients with active UC. If our research findings in mouse IBD models can be successfully translated to humans, it will benefit IBD patients in the near future.

1.4 Clinical Data to Date

This is the first clinical trial to date examining the role of TUDCA in ulcerative colitis patients. However, several clinical trials in other disorders have been completed or are ongoing.

https://clinicaltrials.gov/ct2/results?cond=&term=tudca&cntry=&state=&city=&dist=

1.5 Dose Rationale and Risk/Benefits

A weight based regimen for TUDCA will be used, administering it in 3 divided doses which corresponds to an average dose of 20-25 mg/kg/day accordingly using 1750 mg daily for patients <75 kg and 2000 mg daily for patients ≥75 kg.

It has been shown that TUDCA at the dose of 25mg/Kg/day can achieve maximum composition in the serum and bile in patients with primary biliary cirrhosis¹⁹. Previous clinical studies also have shown that 1 to 6 months of TUDCA treatment with 1750mg/day is efficacious and safe in patients with different diseases, including primary biliary cirrhosis^{19, 27, 28}, liver cirrhosis²⁹, HCV-related chronic hepatitis³⁰ and insulin resistance¹⁷. Animal studies also suggest that TUDCA appears to be very well tolerated even at high doses.

Patients will not be charged for the drug. This will be supplied in original packaging by Bruschettini Srl, Genoa, Italy. TUDCA distribution will be carried out by our Investigational Pharmacy at Washington University. Patients will receive a 6 week supply at initiation visit.

2 Study Objectives

Intestine biopsy samples from inflamed and adjacent non-inflamed intestine tissues before and after the TUDCA treatment will be harvested to evaluate ER stress status by western-blotting for ER stress induced proteins, qRT-PCR and immunochemistry staining. The disease severity will be measured by the Geboes histology index and the complete Mayo score before and after the TUDCA treatment will be monitored. The **overall goal** of this project is to determine if the research findings in mouse IBD models can be successfully translated to humans and thereby provide an adjunctive to optimize therapeutic options in IBD patients focused on the epithelium and with a desirable safety profile. To address this, we propose the following **Specific Aims**:

SA 1. Determine the effect of TUDCA treatment on ER stress in colon biopsy tissues from subjects with symptomatic ulcerative colitis as a primary endpoint.

We expect that TUDCA treatment will reduce ER stress in colon biopsy tissues from subjects with symptomatic ulcerative colitis (UC), as judged by expression levels of ER stress markers. As a primary study endpoint, we will assess:

A. The primary endpoint will be the change in ER stress markers, including eIF2α phosphorylation, XBP1s and BIP/GRP78, in colon biopsy tissues before and after 6 weeks of TUDCA treatment.

SA 2. Measure the safety and tolerance as well as efficacy of TUDCA treatment in symptomatic ulcerative colitis as secondary end points.

We expect that TUDCA treatment will alleviate the UC mucosal inflammation and symptoms and be well tolerated. To assess these secondary endpoints we will:

[figure not shown]
- A. Actively monitor UC study patients for TUDCA safety and tolerability.
- B. Examine efficacy endpoints endoscopic mucosal healing, clinical response (Mayo Score) as well as histologic severity.

2.1 General Design

Figure 1. Trial schema

Type of Study: Open-label clinical trial where all patients receive TUDCA at 1.75 or 2g/day for 6 weeks, divided into three doses, after meals.

Schematic of Trial Design: A total of 12 individuals with active ulcerative colitis and endoscopic evidence of inflammation will be eligible to participate in this open-label clinical trial using TUDCA (adjunct or primary therapy) at 1.75 or 2g/day for 6 weeks, divided into three doses, after meals as summarized in Figure 1. A full schedule of visit assessments and procedures is defined in Table 1 in Section 5.

Duration of Subject Participation: 6 weeks on Trial + 2 weeks Follow up = 8 weeks.

2.2 Primary Study Endpoints

As the primary study endpoint, we will assess the change in ER stress markers, including $eIF2\alpha$ phosphorylation, XBP1s and BIP/GRP78, in colon biopsy tissues before and after 6 weeks of TUDCA treatment.

BIP, XBP1 splicing, phosphorylated eIF2 α will be assessed by Western blot and RT-PCR and immunohistochemistry (IHC). Other ER stress markers, such as PERK, ATF4, CHOP, IRE1 α and ATF6 α will also be examined. In addition, we expect that cell death markers in colon biopsy tissues will also be downregulated, including cJUN, JNK, cleaved caspase 2 and cleaved caspase 3. We will also monitor expression of inflammatory cytokines, IL-1B, TNF α , IL-6 and IFN γ . Additional samples aliquots will be saved (flash frozen and RNAlater) for future studies evaluating adaptive and innate immune readouts.

2.3 Secondary Study Endpoints

- 1. Safety and Tolerance of TUDCA in Ulcerative Colitis patients
- 2. Efficacy of TUDCA treatment in symptomatic ulcerative colitis based on endoscopic mucosal healing, clinical response (Mayo Score) as well as histologic severity (Geboes histology index).

3 Subject Selection and Withdrawal

3.1 Inclusion Criteria

- 1) Ages Eligible for Study: 18 Years to 65 Years;
- 2) Confirmed ulcerative colitis disease through radiographic, endoscopic and/or histologic criteria;
- 3) Confirmed with active ulcerative colitis (defined as a complete Mayo score \geq 5 with endoscopic subscore of \geq 1) See Appendix for Mayo Score using recent adaptation to include any friability on endoscopy to be scored as "2".
- 4) On a stable dose of medications for IBD (i.e. no change in medication within 4 weeks of study enrollment) and not planning to initiate new medication other than TUDCA.

3.2 Exclusion Criteria

- 1) Those that received other chemical chaperone therapies in the 3 months prior to screening;
- 2) Individuals accompanied by gallstones, other intestinal disorders or cancers, or any possible cholestatic pathologies that could alter the enterohepatic circulation of the bile acids, including previous cholecystectomy or short bowel syndrome;
- 3) Subjects with alcohol or drug abuse within the recent year;
- 4) Serious heart, lung, kidney, digestive, nervous, mental, or autoimmune diseases
- 5) Those with plans for abdominal surgery;

- 6) Those unable or unwilling to provide informed consent or failure to comply with the test requirements;
- 7) Pregnant, lactating women;
- 8) Those receiving or planning to receive medicines that inhibit the absorption of the bile acids in the intestine;
- 9) All female subjects must have birth control and not plan to become pregnant during the study. As TUDCA may interfere in the absorption of oral contraceptives, the acceptable methods of birth control should include abstinence or 2 of the following intrauterine device (IUD-with or without local hormone release), diaphragm, spermicides, cervical cap, contraceptive sponge, and /or condoms.
- 10) Subjects with baseline liver transamines (AST or ALT) > 1.5X the upper limit of normal.
- 11) Patients with complete biliary obstruction and known hypersensitivity or intolerance to TUDCA or any of the components of TudcabilTM (or to other bile acids).
- 12) Patients with moderate-to-severe hepatic impairment.
- 13) Evidence of worsening liver function based on the 2 initial laboratory values used to establish the baseline. See Section 6.2.

3.3 Subject Recruitment and Screening

Recruitment: Division of Gastroenterology at Washington University: More than 2500 patients with IBD annually are cared for by the Division's IBD specializing gastroenterologists (n=10). The division actively participates in IBD clinical trials (8 in 2016 alone) and has an established infrastructure for recruitment and execution of new studies examining IBD specific medications. As a leading center for IBD patients sample Biobanking, the Washington University IBD Division also has a robust infrastructure for acquiring and rapidly processing research quality IBD specimens including serum samples, stool and biopsy material. Two of the Washington University site PIs (Drs. [name] and [name]) have worked in the field of IBD for more than 10 years. We anticipate enrolling 2-3 patients per month.

Screening:

Medical examination. All subjects will be screened with a detailed history and physical examination, pregnancy test (*if female*) and laboratories including CBC, complete metabolic panel with a liver panel, C-reactive protein and fecal calprotectin.³¹

3.4 Early Withdrawal of Subjects

3.4.1 When and How to Withdraw Subjects

Subjects may be withdrawn from the study prior to the expected completion if that subject is deemed by the treating physician and study PI to have an adverse reaction to TUCDA (safety reasons and/or disease worsening), failure of the subject to adhere to

protocol requirements or if consent is withdrawn by the subject. The subjects will be informed orally and in writing that they are free to withdraw from the study at any time with no bias or prejudice.

3.4.2 Data Collection and Follow-up for Withdrawn Subjects

Even though subjects may be withdrawn prematurely from the study, we will collect all data available up until the point of withdrawal and at least confirm all survival data for two weeks after the final visit and attempts should be made to obtain permission to record at least survival data up to the protocol-described end of subject follow-up period. This will include at least 4 phone calls to subject, phone calls to next-of-kin if possible and sending of a certified letter. Of note, given the recognized safety of TUDCA, we do not in any way anticipate any risk of mortality, this is only for completeness of protocol.

4 Study Drug

4.1 Description

Tauroursoursodeoxycholic acid, brand name Tudcabil™ is a naturally occurring bile salt proven to reduce ER stress both *in vitro* and *in vivo*, dramatically decreases the clinical, histological and biochemical signs of inflammation in four different IBD mouse models through reducing ER stress in colonic IECs⁴. TUDCA has been tested in many clinical trials for other disease conditions and its safety in humans has been proven. Subjects will receive capsules containing 250 mg of TUDCA provided by Bruschettini Srl, Genoa, Italy which will be administered through our investigational pharmacy. The consituents other than TUDCA are microcystalline cellulose, lactose, corn starch and magnesium stearate

4.2 Treatment Regimen

A weight based regimen for TUDCA will be used, administering it in 3 divided doses which corresponds to an average dose of 20-25 mg/kg/day accordingly using 1750 mg daily for patients <75 kg and 2000 mg daily for patients ≥75 kg.

It has been shown that TUDCA at the dose of 25mg/Kg/day can achieve maximum composition in the serum and bile in patients with primary biliary cirrhosis¹⁹. Previous clinical studies also have shown that 1 to 6 months of TUDCA treatment with 1750mg/day is efficacious and safe in patients with different diseases, including primary biliary cirrhosis^{19, 27, 28}, liver cirrhosis²⁹, HCV-related chronic hepatitis³⁰ and insulin resistance¹⁷. Animal studies also suggest that TUDCA appears to be very well tolerated even at high doses.

Patients will not be charged for the drug. This will be supplied in original packaging by Bruschettini Srl, Genoa, Italy. TUDCA distribution will be carried out by our Investigational Pharmacy at Washington University. Patients will receive a 6 week supply at initiation visit.

4.3 Method for Assigning Subjects to Treatment Groups

Open label study. All patients will receive TUDCA.

4.4 Preparation and Administration of Study Drug

Please see TUDCA related manufacturing information from Bruschettini Srl.

No additional preparation of the study drug will be necessary. Bruschettini Srl, Genoa, Italy will supply our investigational pharmacy with 250 mg capsules in bottles of 120 capsules (15 day supply). The study drug will be distributed by our investigational pharmacy.

4.5 Subject Compliance Monitoring

Subjects will be addressed at the time points described for the study visits for compliance. A final outcome will be determined by study staff at the in-person visits. Subjects not achieving 90% compliance will be subject to withdrawal from the study.

4.6 Prior and Concomitant Therapy

Patients may be on any concomitant therapies as needed for their ulcerative colitis or other conditions. However, patients should not start any new medication that modifies ER stress. It is also not allowed to start any other new therapies for ulcerative colitis.

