We anticipate that TUDCA therapy will reduce ER stress and promote mucosal healing. As TUDCA has the potential to increase stool frequency, it is important to measure efficacy through objective measures (endoscopy and histology) as well as clinical symptoms. Thus, we will obtain a complete Mayo UC score at weeks 0 and 6 and a partial (no endoscopic subscore) at weeks 2 and 4.32 Biopsies will be obtained at both

endoscopic procedures and objectively scored by the Goebes index. Thus, secondary endpoints will include the following using FDA recommended UC Clinical trial guidelines⁴¹:

- 1) Mucosal Healing: A decrease of at least 1 point on the Mayo endoscopic subscore with a final score of 0 or 1 will be used as a marker of mucosal healing.
- 2) Clinical Response: A decrease in Mayo Score of ≥ 3 points and a decrease in Mayo Score of ≥ 30% from baseline and a decrease in the rectal bleeding score of ≥ 1 or an absolute rectal bleeding score of 0-1.
 - a. Clinical Remission will also be recorded if achieved as defined by a total Mayo Score of ≤2 with no subscore >1 and improvement of endoscopic appearance of the mucosa (Mayo 0 or 1).
- **3) Histologic activity:** *Histologic disease activity.* Colon biopsy samples will be harvested and fixed as described. H&E stained sections will be evaluated for tissue damage and inflammation by a gastrointestinal pathologist in a double-blinded manner, using the simplified Geboes histology index^{34, 35}

We expect that TUDCA treatment will significantly alleviate inflammation in colon tissues, which will be correlated with increased plasma concentration of TUDCA or the deconjugated form UDCA. We will collect stool samples both before and after TUDCA treatment for potential (longer range) studies of gut microbiota composition.

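### The plan does not say whether an existing UC drug may be increased during the 6 weeks, and no analysis rule stops later improvement being credited to TUDCA

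*Combined protocol and SAP*

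**What the plan says.** **Entry (3.1, criterion 4).** The patient must be "On a stable dose of medications for IBD (i.e. no change in medication within 4 weeks of study enrollment") and must have no plan to start a medication other than TUDCA.

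**During treatment (4.6).** "Patients may be on any concomitant therapies as needed for their ulcerative colitis or other conditions". Two limits follow: "patients should not start any new medication that modifies ER stress", and "It is also not allowed to start any other new therapies for ulcerative colitis". Both concern starting a drug. Neither mentions the dose of a drug already in use.

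**Withdrawal (4.8.5).** Use of a prohibited concomitant drug is one of six grounds on which a patient may, at discretion, be withdrawn. Whether a dose increase is prohibited is not stated.

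**Design (2.1, 4.3).** Patients take "TUDCA (adjunct or primary therapy) at 1.75 or 2g/day for 6 weeks", so background UC treatment is expected in at least some of them. There is no comparator: "Open label study. All patients will receive TUDCA".

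**Outcomes and analysis (6.1, 6.2).** Clinical response begins with "A decrease in Mayo Score of ≥ 3 points and a decrease in Mayo Score of ≥ 30% from baseline" and adds a rectal-bleeding condition. Remission and mucosal healing are also defined from Mayo scores alone. The marker analysis contrasts values before and after treatment. None of these rules refers to background medication.

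**The concern.** In a single-arm before/after trial, everything that changes between the two endoscopies is part of the estimated effect. If a patient's existing UC drug is increased in week 3 and the Mayo criteria are met at week 6, the definitions as written make that patient a TUDCA responder.

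Such increases are unlikely to fall at random. It is reasonable to assume that they go mainly to patients who are not improving, so the bias would tend to move patients from failure to success. The protocol itself expects that symptoms may worsen in some patients, because 6.2 notes that TUDCA could aggravate diarrhea.

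The primary endpoint is exposed as well. Section 1.1 states that inflammatory stimuli can cause ER stress, so a stronger anti-inflammatory background could lower the markers without any contribution from TUDCA.

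**Working it through.** **Step 1: does any section settle the question?**

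- 3.1 is applied at entry. Its four-week window most naturally looks back from enrollment. Even if it is read as also running forward four weeks, it would end by week 4 at the latest, before the week 6 endoscopy. Its forward-looking clause covers only starting new medication.
- 4.6 restricts starting, not dose. An increase in a drug already taken is neither clearly allowed nor barred.
- 4.8.5 depends on what counts as prohibited, which leads back to 4.6, and it is discretionary.
- 6.1 and 6.2 contain no rule for a change in background therapy.

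The documents are therefore silent on dose changes, and the analysis does not deal with them if they happen.

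**Step 2: is there a figure in the plan to reproduce?** There is none for this point: no rate of dose changes and no expected response rate is given. The sample sizes in Table 2 (5.09 and 6.39, rounded up to 7) do reproduce with a two-sample t-test, two-sided 5%, difference/SD = 0.52/0.26 = 2.0, but nothing here depends on them. The one input used is the planned enrollment of 12 (6.1).

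**Step 3: weight of one patient.** 1/12 = 8.3 percentage points, if that patient would otherwise have failed and the denominator is 12. The plan does not fix the denominator. With only the 7 patients that 6.1 calls sufficient, it would be 1/7 = 14.3 points.

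**Step 4: illustration for the response rate (assumed inputs).** Let k of 12 patients have an increase, p0 be the response probability without it and p1 the probability with it. The expected observed rate is ((12 − k)·p0 + k·p1)/12. For example, k = 2, p0 = 0.2, p1 = 0.5 gives (2.0 + 1.0)/12 = 25%.

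| k | p0 = 0.2, p1 = 0.5 to 1.0 | p0 = 0.3, p1 = 0.5 to 1.0 |
|---|---|---|
| 0 | 20% | 30% |
| 2 | 25% to 33% | 33% to 42% |
| 3 | 28% to 40% | 35% to 48% |
| 4 | 30% to 47% | 37% to 53% |

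**Step 5: illustration for a marker (assumed inputs).** Take 12 within-patient changes, normally distributed, with no TUDCA effect. In k patients the increase lowers the marker by 1 to 2 SD of the change. A paired t-test at two-sided 5% should show a significant decrease 2.5% of the time. In 200,000 simulated trials per setting, the frequency was:

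- k = 2: about 6% to 8%
- k = 3: about 9% to 15%
- k = 4: about 13% to 27%

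**The case against.** The case on the other side has four parts.

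- **Silence is not permission.** 4.6 says what patients may be on. It does not say that doses may be changed, and a site could take the stable-dose criterion together with the ban on new UC therapies to mean that increases are barred. This stands. A reader might infer that the protocol expressly permits dose increases; the text does not support that. But two sites, or two clinicians at this single center, could read it differently, and that is a reason to settle it.
- **Little hangs on the response rate.** Efficacy is secondary, is to be reported in qualitative terms, and has no threshold or go/no-go rule. This stands and limits the consequence. It does not remove it: 6.2 also plans tests between time points and sets responder definitions that yield a rate, and the primary marker contrast has the same gap.
- **There are brakes.** 3.4.1 allows withdrawal for disease worsening. Under 7.4, a Mayo increase of more than 3 points leads to TUDCA dose reduction and then to discontinuation if symptoms persist. These cover clear worsening but not ordinary lack of improvement, and under 4.8.4 patients who stop the drug should still have final assessments.
- **Healing is slow.** 6.2 says that mucosal healing can take months. A mid-study increase is therefore less likely to create apparent endoscopic healing than apparent symptomatic response. This stands.

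**Conclusion.** The point holds as a gap in both the conduct rule and the analysis rule. The protocol leaves on-study increases of existing UC drugs unaddressed, and the outcome definitions, followed literally, would credit any resulting improvement to TUDCA with no control arm to reveal it.

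The size is unknown. The 8.3 points per patient assumes a denominator of 12 and a patient who would otherwise have failed. The ranges in the working rest on assumed numbers of patients and assumed effects, none of which is in the documents. A reader might go further and infer that the trial's efficacy results will be inflated by some stated amount. The documents do not support that, because they do not show that any increase will occur.

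It is worth correcting before results are seen, because the trial is open label and a rule chosen afterwards could be influenced by them.

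**What to change.** 1. **Reconcile 3.1, 4.6 and 4.8.5** so that they state whether an on-study increase in an existing UC drug is a prohibited change. Which way to decide is a clinical matter for the sponsor.
2. **Record the date and dose of any change** in a background UC drug. Table 1 already has concomitant medication reviewed at screening, baseline and weeks 2, 4 and 6, so this needs only a flag on that form.
3. **Add a rule to 6.2:** a patient whose background UC drug is increased counts as not responding, not in remission and not healed from then on.
4. **Markers and Geboes score:** keep all patients in the main before/after analysis, and add a sensitivity analysis that excludes samples taken after an increase.

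**Cost.** A short protocol clarification, one form flag and two sentences of analysis text. Reported response rates may be lower. The sensitivity analysis has fewer patients and selects on an event after baseline. It may favor TUDCA, because it drops patients who were doing badly, so it should be read only beside the all-patient result.
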